## 4 Change to protocol specified analyses

Analyses changed as noted in change history due to the early termination of the study.

## 5 Appendix

## 5.1 Imputation rules

## 5.1.1 Study drug

Any partial dates will be imputed as follows:

We take the earlier day of

- The last day in the month and
- The end day of the corresponding epoch

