## 1.1 Study design

CAIN457O12301 is a randomized, double-blind, placebo-controlled Phase III study over 24 weeks in participants with moderate to severe Rotator Cuff Tendinopathy (RCT), refractory to Standard of Care (SoC) (Non-Steroidal Anti-Inflammatory Drugs (NSAIDs) course as per local standard practice, if not intolerant or contraindicated, and a course of physiotherapy over a period of 8 weeks).

A screening period of up to maximum of 56 days will be used to assess participant eligibility. During the 2-week run-in period prior to the Baseline (BSL) visit, the participant will need to have 2 weeks of stable NSAID intake and standardized physiotherapy.

During Study period 1 (BSL to Week 16), double-blinded treatment is administered over 12 weeks, reflecting 16 weeks of total drug exposure. Approximately 234 eligible participants were planned to be randomized at BSL in a 1:1 ratio to one of the following arms:

- Arm 1 (N=117): secukinumab 300 mg s.c. at Day 1 and Weeks 1, 2, 3, 4, 8, and 12
- Arm 2 (N=117): placebo at Day 1 and Weeks 1, 2, 3, 4, 8, and 12

Randomization will be stratified by tear status (no tear/partial tear).

The last dose of study treatment will be administered at Week 12; the primary outcome assessments will be performed at Week 16.

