#### 2.1.1.2 Study Day 1 and other study days

The first day of administration of randomized study treatment (first dose) is defined as *Study Day 1* or *Day 1*.

Of note, if there has been no drug administration, the randomization day is defined as Day 1.

All other study days will be labeled relative to Day 1. For event dates on or after Day 1, study day for a particular event date is calculated as [Date of event] – [Date of first dose] + 1, i.e., Day 2, Day 3, etc., will be one day, two days, etc., after Day 1, respectively. For the dates before Day 1, study day for an event date is calculated as [Date of event]. [Date of first dose] is a

Day 1, study day for an event date is calculated as [Date of event] – [Date of first dose], i.e., Day -1, Day -2, etc., will be one day, two days, etc., before Day 1, respectively. Duration of an event will be calculated as (Event end date – Event start date + 1).

The descriptor "Day 0" will not be used.

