#### 2.4.1.1 Analysis visit window

Analysis visit windows will be used for the data that is summarized by visit; they are based on the study visit and evaluation schedule and comprise a set of days around the nominal visit day. For any assessment, there are protocol defined scheduled visits around which analysis visit windows were created to cover the complete range of days within the study. Visit windows will vary depending on the frequency of the analysis visit. The analysis visit windows are defined in Table 2-1. In the tables, the days are counted since the first dose of the study treatment (i.e., Study Day 1).

When visit windows are used, all visits will be re-aligned, i.e., they will be mapped into one of the visit windows. E.g., if the *Week 4* visit of a participant is delayed and occurs on Day 46 instead of on Day 29, it will be re-aligned to visit window *Week 8*. In the case of major deviations from the visit schedule, or due to unscheduled visits, several assessments of a participant may fall in a particular visit window (either scheduled or unscheduled). Statistical approaches to handle multiple assessments in a given visit window are specified below.

In general, if two consecutive visits  $V_t$  and  $V_s$  are x days apart (t < s), when x is even, the upper limit for  $V_t$  will be  $V_t + x/2$  and the lower limit for  $V_s$  will be ( $V_s - x/2$ ) + 1; when x is odd, x/2 is rounded down to integer y, then the upper limit of the visit window for  $V_t$  will be  $V_t + y$  and the lower limit for the visit  $V_s$  will be  $V_s - y$ . The algorithm needs to ensure that visit windows are not overlapping and there are no gaps, such that each assessment can be uniquely allocated to one visit window, e.g., if Week 8 visit is scheduled at day 57, Week 12 visit is scheduled at day 85 and Week 16 visit is scheduled at day 113, then the visit window for week 12 extends from Day 72 to Day 99.

Of note, participants are allowed to have gaps in visits.

Table 2-1 Analysis visit windows

Analysis Visit	Target Day	Analysis Visit Window	Group 1	Group 2	Group 3	Group 4	Group 5	Group 6	Group 7
Baseline	1*	≤ 1	≤ 1				≤ 1	≤ 1	≤ 1
Week 1	8	2-11							
Week 2	15	12-18	2-22						2-22

Analysis Visit	Target Day	Analysis Visit Window	Group 1	Group 2	Group 3	Group 4	Group 5	Group 6	Group 7
Week 3	22	19-25							
Week 4	29	26-43	23-43				2-71		23-43
Week 8	57	44-71	44-71						44-71
Week 12	85	72-99	72-99						72-99

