#### 2.7.1 Adverse events (AEs)

All information obtained on adverse events will be displayed by treatment group and participant.

The number (and percentage) of participants with treatment emergent adverse events will be summarized in the following ways:

- by treatment, primary system organ class and preferred term.
- by treatment, primary system organ class, preferred term and maximum severity.

Confidence intervals for the crude rate will be derived as described in Section 5.4.

Treatment emergent adverse events are defined as events started on or after the first dose of study medication or events present prior to the first dose of study medication but increased in severity on or after dosing based on preferred term and within last dose + 84 days (inclusive).

A participant with multiple adverse events within a primary system organ class is only counted once towards the total of the primary system organ class.

Separate summaries will be provided for study treatment related adverse events, death, serious adverse event, other significant adverse events leading to discontinuation and adverse events leading to dose adjustment or interruption.

Adverse events reported will be presented in descending frequency according to its incidence in the AIN457 300 mg group starting from the most common event. AEs will be summarized by presenting the number and percentage of participants having any AE, having an AE in each primary system organ class and having each individual AE (preferred term).

Summaries will also be presented for AEs by severity and for study treatment related AEs. If a particular AE 'severity' is missing, this variable will be listed as missing and treated as missing in summaries. If a participant reported more than one adverse event with the same preferred term, the adverse event with the greatest severity will be presented. If a participant reported more than one adverse event within the same primary system organ class, the participant will be counted only once with the greatest severity at the system organ class level, where applicable. Of note, AEs by severity will be provided by SOC in the study report and AEs by severity and PTs may be provided if required at ad-hoc basis.

The MedDRA version (version 27.0 or above) used for reporting the study will be described in a footnote.

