In addition, exposure time-adjusted incidence rates including 95% confidence intervals will be provided for the entire study period following the guideline as below:

- Primary SOC level for AE and SAE
- RMP risks
- PT level for SAE
- Overall PT level for AE and SAE
- Other selected AEs on lower levels (e.g., PT), if appropriate

Algorithms for date imputations are provided in Section 5.1.2.

Non-treatment emergent adverse events will be flagged on the overall AE listing. These adverse events occurred before the first dose of the study treatment or after 84 days post the last dose.

An overview of the safety analyses (i.e., crude incidence, exposure time-adjusted incidence) which will be performed for adverse events and other binary safety variables (e.g., labs and vital signs) for each analysis period is described in Table 2-3.

Table 2-3	Overview of analyses on some safety endpoints								
Analysis period	AEs & SAEs	RMP risks	AEs by severity	Study drug related AEs	Notables (vitals/lab)				
Entire Study	

crude incidence

	
 
crude incidence
 
	
 
crude incidence
 
	

crude incidence

	

crude incidence

				
	
 
exposure time adjusted incidence
 
	
 
exposure time adjusted incidence
 
							

Table 2-3 Overview of analyses on some safety endpoints

For the legal requirements of ClinicalTrials.gov and EudraCT, two required tables on **ontreatment/treatment emergent** adverse events which are not serious adverse events with an incidence greater than z% and on **on-treatment/treatment emergent** serious adverse events and SAE suspected to be related to study treatment will be provided by system organ class and preferred term on the safety set population. Here threshold value z is set to 2 (%) but it may be updated following review of the dry run outputs.

If for a same participant, several consecutive AEs (irrespective of study treatment causality, seriousness and severity) occurred with the same SOC and PT:

- a single occurrence will be counted if there is  $\leq 1$  day gap between the end date of the preceding AE and the start date of the consecutive AE
- more than one occurrence will be counted if there is > 1 day gap between the end date of the preceding AE and the start date of the consecutive AE

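### SAP 5.1.1 sends any partial study-drug date to the latest eligible day; for a first dose this moves Day 1 late, by up to about 7 days when the Week 1 dose date is known

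*SAP*

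**What the plan says.** SAP 5.1.1, headed only as study drug, opens with "Any partial dates will be imputed as follows" and takes the earlier of two days: "The last day in the month and" "The end day of the corresponding epoch". It does not separate a first dose from a last dose. It sets no bound from randomization, the Baseline visit or the neighbouring doses. By contrast, SAP 5.1.2 (adverse events) and 5.1.3 (concomitant medication) have separate rules for start and end dates.

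The first dose matters in several places:

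- **Study days and visit windows.** SAP 2.1.1.2: "The first day of administration of randomized study treatment (first dose) is defined as" Day 1. The randomization day is used only if no drug was given. The windows in SAP 2.4.1.1 count from the same day.
- **Exposure.** The formula in SAP 2.4.1 subtracts the first-dose date.
- **Adverse events.** SAP 2.7.1: "Treatment emergent adverse events are defined as events started on or after the first dose of study medication", with a further clause for events that worsen after dosing. Of the non-emergent events it says: "These adverse events occurred before the first dose of the study treatment or after 84 days post the last dose". These are flagged in the listing, while the summary tables cover on-treatment events only (SAP 2.7).

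**The concern.** A latest-date rule is a usual, inclusive choice for a last dose because it keeps events inside the follow-up window. For a first dose it works the other way. It starts the clock after the drug was given, so real post-dose events can be classed as pre-treatment, study days come out too small, and exposure is understated.

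The rule also ignores better information. The first dose is scheduled at the Baseline visit, where randomization takes place (Protocol Table 1-2 and 6.3.1), and the IRT holds the randomization date (Protocol 10.1.5.2). A partial loading-dose date can likewise be placed after later doses whose dates are known.

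**Working it through.** The plan gives no figure on this point, so there is none to reproduce.

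**Inputs**

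- Doses on Days 1, 8, 15, 22, 29, 57 and 85 (SAP 1.1; Protocol Table 1-2).
- Imputed date = min(month end, epoch end) (SAP 5.1.1).
- Study day = date − first-dose date + 1 on or after Day 1, and date − first-dose date before it (SAP 2.1.1.2).
- Windows for WORC and PROMIS (SAP Table 2-1, Group 1): Week 2 is 2–22, Week 4 is 23–43, Week 12 is 72–99, Week 16 is 100–127, Week 20 is 128–155, Week 24 is 156–183.
- Assumptions: only the day is missing, the other doses are on schedule, and the epoch ends at Day 113.

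**Step 1: where the first-dose record lands.** Month end is at most 30 days after the true date and epoch end is 112 days after it, so epoch end gives no protection to a participant who completes the period. Over the 365 possible first-dose dates in 2023, the record is late in 96.7%, by 14.7 days on average. In 73.7% it falls after the planned Week 1 dose. These figures describe the displaced record, not Day 1.

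**Step 2: where Day 1 lands.** Day 1 is the first day of administration, so a known later dose caps the shift:

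shift = min(days to month end, days to next known dose)

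- Week 1 date known: at most 8 − 1 = 7 days. In 2023 (seven months of 31 days, four of 30, one of 28) the full 7 days applies to 7×24 + 4×23 + 21 = 281 of 365 start dates (77.0%). The mean shift is (7×281 + 12×(0+1+…+6))/365 = (1,967 + 252)/365 = 6.1 days.
- Week 1 absent or also partial, Week 2 date known: at most 15 − 1 = 14 days.
- No known dose date before month end: up to 31 − 1 = 30 days.

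**Step 3: one example.** The true first dose is 3 Oct 2023 with the day missing, and the Week 1 dose is known to be 10 Oct. The first-dose record goes to 31 Oct, and Day 1 becomes 10 Oct. An adverse event with a complete start date of 5 Oct (true Day 3) becomes Day −5 and is not treatment-emergent by its start date. With the last dose on Day 85 and the last visit on Day 169, exposure falls from 169 − 1 + 1 = 169 days to 169 − 8 + 1 = 162 days.

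**Step 4: visit windows**

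| True day | Shift 7 | Shift 14 | Shift 30 |
|---|---|---|---|
| 29 (Week 4) | 22, Week 2 | 15, Week 2 | −2, Baseline |
| 113 (Week 16) | 106, Week 16 | 99, Week 12 | 83, Week 12 |
| 141 (Week 20) | 134, Week 20 | 127, Week 16 | 111, Week 16 |
| 169 (Week 24) | 162, Week 24 | 155, Week 20 | 139, Week 20 |

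At 13 days the Week 16 visit is Day 100, still in its window, so the threshold is 14. At 7 days only the Week 4 visit is relabelled, and it carries no primary or secondary efficacy endpoint.

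**Step 5: which adverse events are affected.** Under SAP 5.1.2, an event with a partial start in the treatment-start month and no earlier end date is set to treatment start + 1 day and stays treatment-emergent. Events that worsen after the imputed date also stay. Two kinds lose their status: events with a complete start date in the shifted days, and events whose end date precedes the imputed first dose.

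**Step 6: a loading dose.** Take the same participant with the first dose known and the 10 Oct dose partial. That dose goes to 31 Oct, after the known doses of 17 and 24 Oct and on the same day as the Week 4 dose. Day 1 and the last dose do not change, so the error stays in the dosing record.

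**The case against.** The strongest reply is that the trigger is hardly credible. The first dose is scheduled at the Baseline visit, home dosing is offered only at Weeks 1 and 3 (Protocol 1.3 and 4.1), all dosing dates and times go on a dedicated eCRF page (Protocol 6.4), and missing values are queried (Protocol 10.1.5.2). The rule was perhaps meant for last-dose dates only. The study stopped early, with 21 randomized at termination and no superiority testing (SAP 1 and 2.5.2), so a misplaced visit could not alter a test result. All of this stands as to frequency and consequence. It does not change the text, which covers every partial date and gives a programmer no other instruction for a first dose. Safety tables and exposure-adjusted rates are still planned.

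A reader might infer something stronger: that Day 1 routinely moves by up to a month, past known loading doses, and relabels the primary Week 16 assessment. The documents do not support that. Under SAP 2.1.1.2 a known dose cannot precede the first day of administration, so an on-schedule Week 1 date holds the shift to 7 days. Nor are early adverse events lost in general, as Step 5 shows. The month-end rule for a last dose is also not a fault in itself: it keeps more events inside the 84-day window, and exposure is capped at the last visit (SAP 2.4.1).

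**Conclusion.** The point holds as a minor specification error. As written, SAP 5.1.1 can date the first dose too late:

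- by up to 7 days when the Week 1 dose date is known and on schedule (6.1 days on average over 2023 start dates);
- by 14 days or more only if the Week 1 dose is also partly dated, late or absent;
- by up to 30 days only if no later dose was given or the later dose dates are partial too.

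Within that range, study days and exposure are wrong and some early adverse events leave the treatment-emergent tables. The primary Week 16 visit is safe below 14 days.

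These sizes assume a known month and year. If the month is missing as well, month end is undefined and only epoch end remains. Nothing in the documents shows that a partial first-dose date occurred. One affected participant would be 1/21 = 4.8% of those randomized at termination, or somewhat less if participants already screened were added.

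**What to change.** Replace the single rule in SAP 5.1.1 with three:

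1. **First dose.** Impute a partial date as the randomization/Baseline visit date, provided that it agrees with the known month and year and is not after the next known dose.
2. **Other doses.** Use the visit date where there is one, and in all cases keep the imputed date between the preceding and following known dose dates. The bounds matter most for home doses at Weeks 1 and 3, where dispensing may come before administration.
3. **Last dose.** Keep the earlier of month end and epoch end only where no visit or IRT date exists.

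The cost is a few lines of SAP text and code, using dates already held in the eCRF and IRT. No analysis is lost, and nothing changes for participants with complete dosing dates.

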## 5.1.2 AE date imputation

Impute AE end date:

- 1. If the AE end date 'month' is missing, the imputed end date should be set to the earliest of the (min (last visit date, last dose date + 84 days), 31DECYYYY, date of death).
- 2. If the AE end date 'day' is missing, the imputed end date should be set to the earliest of the (min (last visit date, last dose date + 84 days), last day of the month, date of death).
- 3. If AE 'year' is missing or AE is ongoing, the end date will not be imputed.

Impute AE start date:

Before imputing AE start date, find the AE start reference date as below

- If the (imputed) AE end date is complete and the (imputed) AE end date < treatment start date then AE start reference date = min (informed consent date, earliest visit date).
- Else AE start reference date = treatment start date
- 1. If the AE start date 'year' value is missing, the date uncertainty is too high to impute a rational date. Therefore, if the AE year value is missing, the imputed AE start date is set to NULL.
- 2. If the AE start date 'year' value is less than the treatment start date year value, the AE started before treatment. Therefore:
  - a. If AE 'month' is missing, the imputed AE start date is set to the mid-year point (01JulYYYY).
  - b. Else if AE 'month' is not missing, the imputed AE start date is set to the midmonth point (15MONYYYY).
- 3. If the AE start date year value is greater than the treatment start date year value, the AE started after treatment. Therefore:
  - a. If the AE month is missing, the imputed AE start date is set to the year start point (01JanYYYY).
  - b. Else if the AE month is not missing, the imputed AE start date is set to the later of (month start point (01MONYYYY), AE start reference date + 1 day).

4. If the AE start date year value is equal to the treatment start date year value:

- a. And the AE month is missing the imputed AE start date is set to the AE reference start date + 1 day.
  - b. Else if the AE month is less than the treatment start month, the imputed AE start date is set to the mid-month point (15MONYYYY).
  - c. Else if the AE month is equal to the treatment start date month or greater than the treatment start date month, the imputed AE start date is set to the later of (month start point (01MONYYYY), AE start reference date + 1 day).

If complete (imputed) AE end date is available and the imputed AE start date is greater than the (imputed) AE end date, then imputed AE start date should be set to the (imputed) AE end date.

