## 2.7 Safety analyses

All safety analyses will be based on the SAF and performed on treatment received or actual treatment as described below:

The actual treatment or treatment received for summaries of safety data will differ to the treatment assigned at randomization only if a participant received the wrong treatment during the entire study.

For those participants who did not receive the randomized treatment, i.e., who received erroneously the wrong treatment at least once, an additional AE listing will be prepared displaying which events occurred after the treatment errors.

Safety summaries will include only data from the on-treatment period except for baseline data which will also be summarized where appropriate (e.g., change from baseline summaries). In addition, a separate summary for death including on treatment and post treatment deaths will be provided. In particular, summary tables for adverse events (AEs) will summarize only on-treatment events, with a start date during the on-treatment period (treatment-emergent AEs).

The on-treatment period lasts from the date of first administration of study treatment up to last administration + 84 days.

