#### Impute CM start date:

- 1. If the CM start date year value is missing, the imputed CM start date is set to one day prior to treatment start date.
- 2. If the CM start date year value is less than the treatment start date year value, the CM started before treatment. Therefore:
  - a. If the CM month is missing, the imputed CM start date is set to the mid-year point (01JulYYYY).
  - b. Else if the CM month is not missing, the imputed CM start date is set to the mid-month point (15MONYYYY).
- 3. If the CM start date year value is greater than the treatment start date year value, the CM started after treatment. Therefore:
  - a. If the CM month is missing, the imputed CM start date is set to the year start point (01JanYYYY).
  - b. Else if the CM month is not missing, the imputed CM start date is set to the month start point (01MONYYYY).
- 4. If the CM start date year value is equal to the treatment start date year value:
  - a. And the CM month is missing or the CM month is equal to the treatment start date month, then the imputed CM start date is set to one day prior treatment start date.
  - b. Else if the CM month is less than the treatment start date month, the imputed CM start date is set to the mid-month point (15MONYYYY).
  - c. Else if the CM month is greater than the treatment start date month, the imputed CM start date is set to the month start point (01MONYYYY).

If complete (imputed) CM end date is available and the imputed CM start date is greater than the (imputed) CM end date, then imputed CM start date should be set to the (imputed) CM end date.

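### An adverse event with an unknown start year gets no start date and, on a literal reading, drops out of the treatment-emergent tables even when nothing shows that it ended before dosing

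*SAP*

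**What the plan says.** SAP 5.1.2 first derives an AE start reference date. If the (imputed) end date is complete and precedes treatment, the reference is the earlier of consent and first visit. For all other events, "Else AE start reference date = treatment start date".

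The numbered start-date rules follow. Rule 1 gives its reason, "If the AE start date 'year' value is missing, the date uncertainty is too high to impute a rational date", and then its result: "if the AE year value is missing, the imputed AE start date is set to NULL". It uses neither the end date nor the reference date. Rule 4a covers an event in the treatment-start year with an unknown month and places it at the reference date plus one day. A closing correction moves an imputed start back to the end date if it falls later than that. For end dates, "If AE 'year' is missing or AE is ongoing, the end date will not be imputed".

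SAP 2.7 states that "summary tables for adverse events (AEs) will summarize only on-treatment events, with a start date during the on-treatment period", and defines that period as first dose to last dose plus 84 days. SAP 2.7.1 is wider: it also counts events present before dosing that worsened afterwards. The listing flag in 2.7.1 marks as non-treatment-emergent those events that occurred before first dose or beyond 84 days after the last. Neither section says where an undated event belongs.

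**The concern.** For tabulation, a missing start year raises a yes/no question: could the event have begun on treatment? Unless the event is known to have ended before first dose, the answer is that it could have. Rule 1 followed by the SAP 2.7 filter acts as if the answer were no. In a safety analysis that is the anti-conservative direction, because doubt about a date lowers the count.

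Incidence of AEs and SAEs remains a secondary endpoint after the early termination (SAP Table 1-1), and the registry tables described in SAP 2.7.1 are also restricted to on-treatment events. With arms this small, one omitted event changes a displayed percentage visibly.

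**Working it through.** No figure in the plan depends on this rule, so there is none to reproduce. The check follows example records through the rules and then sizes one lost event.

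**1. Example records.** SAP 5.1.2 start rules and closing correction, then the SAP 2.7 start-date test:

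| Start recorded | End date | Start under SAP 5.1.2 | Passes SAP 2.7? |
|---|---|---|---|
| Complete, after first dose | After first dose | As recorded | Yes |
| Treatment-start year only | After first dose | First dose + 1 day (rule 4a) | Yes |
| Year missing | After first dose | NULL | No |
| Year missing | Ongoing | NULL | No |
| Year missing | Before first dose | NULL | No |

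The closing correction cannot rescue rows 3 and 4, since it needs an imputed start that is later than the end date. The outcome is the same whether a NULL is read as outside the period or sorts before every date. Row 5 is rightly excluded. Rows 2 and 3 show the inconsistency: losing one more date field turns inclusion into exclusion.

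**2. Is the date really too uncertain?** Protocol 8.6.1 defines an AE as occurring after consent and sends earlier conditions to medical history. Screening lasts at most 56 days (SAP 1.1). The start therefore lies between consent and the end date, or the last contact if the event is ongoing. The reference date already separates events that ended before treatment from the rest.

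**3. Size of one lost event.** SAP 1 reports 21 randomized at termination. At 1:1, assume arms of 10 and 11. Crude incidence is x/n, with the continuity-corrected score interval of SAP 5.4.2.1 (z² = 3.8415).

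- n = 10, x = 1, upper limit: [2 + 3.8415 + 1 + 1.96·√(3.8415 + 2 − 0.1 + 0.4·(9 − 1))] / (2·13.8415) = 12.702 / 27.683 = 45.9%
- n = 10, x = 1, lower limit: [2 + 3.8415 − 1 − 1.96·√(3.8415 − 2 − 0.1 + 0.4·(9 + 1))] / 27.683 = 0.145 / 27.683 = 0.5%

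| n | Event lost | Event counted |
|---|---|---|
| 10 | 0% (0 to 34.5%) | 10.0% (0.5 to 45.9%) |
| 11 | 0% (0 to 32.1%) | 9.1% (0.5 to 42.9%) |

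Both counted values exceed the 2% threshold for the registry table of non-serious events. At the planned 117 per arm the shift would be 1/117 = 0.9 points.

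**4. Exposure-adjusted rate.** SAP 5.4.3.1 uses D/T with T the sum of times to first event, and a NULL start gives no time. Assume 10 participants with full exposure of 85 + 84 = 169 days and one event of the term. Dating it at Day 2 gives T = 9·169 + 2 = 1,523 days and a rate of 36,525/1,523 = 24.0 per 100 subject-years. Had it begun on Day 169, T = 1,690 and the rate would be 36,525/1,690 = 21.6. Early dating thus raises the rate by at most 1,690/1,523 − 1 = 11% here, whereas dropping the event makes it zero.

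**The case against.** Several stronger readings are tempting, and the documents do not support them.

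- *The event vanishes from every adverse-event table.* It does not. SAP 2.7.1 displays all AE information by participant, and with so few participants the listing can be read case by case. The death summary in SAP 2.7 covers post-treatment deaths as well.
- *It can never be counted.* The SAP does not say how an undated event is classified. Exclusion follows from the literal wording of SAP 2.7, and the worsening clause of 2.7.1 might admit an event shown to have worsened after dosing.
- *An end date after dosing proves the event was treatment-emergent.* It proves presence, not onset, because the event may have begun in screening. Counting such events is the more cautious convention, not a correction of a known misclassification.
- *The medication rule is a precedent.* SAP 5.1.3 says "If the CM start date year value is missing, the imputed CM start date is set to one day prior to treatment start date". Applied to an AE, that would make the event pre-treatment, so it does not support counting it.

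The defence is also right that a missing year should be very uncommon. The study lasts at most 32 weeks, AEs are sought at every visit with start and end dates (Protocol 8.6.1), missing values are queried (Protocol 10.1.5.2), and SAEs are reported within 24 hours of awareness (Protocol 8.6.3).

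What this leaves standing is a stated rule, not merely a silence, whose plain application removes possibly treatment-emergent events and runs against rule 4a beside it.

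**Conclusion.** The point holds in limited form. SAP 5.1.2 rule 1 ignores the end date. With the literal SAP 2.7 filter it leaves an event of unknown status out of the treatment-emergent AE, SAE and registry tables and out of the exposure-adjusted rate. That is anti-conservative and inconsistent with rule 4a.

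The effect is zero if no start year is missing. If one is, it is about 9 to 10 percentage points for that term in that arm. This assumes arms of 10 or 11, although participants already screened could continue and arms may be larger, and no other dated event of the same term in that participant. The documents give no frequency. The change is worth making because it is cheap, not because the problem is likely to be common.

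**What to change.** Replace start-date rule 1 in SAP 5.1.2 with:

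*If the start year is missing and the (imputed) end date is before first dose, the event is not treatment-emergent. Otherwise set the start to the AE start reference date + 1 day, or to the end date if that is earlier under the existing correction; count the event as treatment-emergent; and flag it as imputed in the listing.*

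This uses a date the section already derives and the same one-day offset as rule 4a, and it covers ongoing events and events with no usable end date. Also reconcile SAP 2.7 (start date only) with 2.7.1 (start or worsening), so that one definition of treatment-emergent governs all tables.

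The cost is one sentence and one code branch. There are two downsides to disclose. An occasional event that began before treatment, or later than last dose plus 84 days, may be counted. Time to first event is also shortened for that participant, which raises the exposure-adjusted rate for the term.
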